## 9.0 Recommendation for Only One Parent Consent

Both this proposed study and the investigational device do not involve greater than minimal risk.

### Rationale for the device:

*Safety of Photobiomodulation:* Photobiomodulation has been extensively studied on humans for more than 30 years, including its use for neurological conditions. There are several photobiomodulation products (for neurological conditions) that are on currently on the market (using both LED and Lasers). The consumers report no side-effects.

After more than three decades of research there are no known major side effects attached to photobiomodulation therapy.

The device has been designated as "Non-Significant Risk" by the FDA.

*Rare Minor Side effects for first time users only include:* Tiredness (temporary) – probably due to the release of metabolites but the majority report a resurgence of energy. Headaches (temporary) – from the reactivation of neural connections and increased microcirculation.

*Safety Issues of our product specifically:* Our product emits non-laser based irradiation (incoherent light) with a low level energy intensity. Infrared emits non-laser based irradiation (incoherent light) with a low level energy intensity. We use 850 nm. The participants might perceive slight warmth. No other perceptions will be produced by wearing the device. No feelings of discomfort are anticipated (the device is especially made for children, it's very comfortable and soothing to wear). There are no known side-effects of photobiomodulation (with 30 years of research and studies, including research on 5 year old children diagnosed with ASD).

Rationale for the study:

The study activities include: 1) wearing the device and / or 2) free play. In addition, the parents will be interviewed about the child's behavior on a weekly basis.

None of these activities present greater than minimal risk to the health and well-being of the participants.

## 10.0 Consent Process

Parents of child participants will be debriefed about the purposes of the study. They will be explained risks and benefits. The researcher will answer all their questions. The participants will review the Informed Consent form. Parents will be given an opportunity to ask questions about the consent. The parents will be explained that they do not have any obligation to participate in the study and their refusal to participate will not affect any current treatment or benefits that they or their child currently receives. This explanation will take place in person, in [name] office, in a private room.

During the conversation, we will ask questions to ensure that the parent understands that the participation is voluntary, that the child may be placed in the placebo group, the time commitment required, the possible risks of being in the study and possible benefits.

Prior to enrolling a child in the study, we will collect the signed Informed Consent from the parents of every participant.

We will not be obtaining consent from the child participants. The reason is as follows: children between the ages 2 to 7 years, especially those diagnosed with ASD, have limited mental capacity and cannot be reasonably consulted about the risks and benefits of the study. Children will be asked to wear a device on their head. Due to their limited level of comprehension and responsiveness, they may not be able to give an affirmative verbal assent.

Nonetheless, if children demonstrate a visible discomfort, or verbally say that they do not want to wear the device, they will not be forced to do it.

- 

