# **Transcranial Photobiomodulation for reducing autism symptoms in children.**

*May 1, 2022*

PROTOCOL TITLE:

Transcranial photobiomodulation for reducing autism symptoms in children.

PRINCIPAL INVESTIGATOR:

Name	[name]
Department	N/A
[contact]

RESEARCHERS:

Name	[name]
Department	N/A
[contact]

Name	[name], CFA, Esq.
Department	N/A
[contact]

Name	[name]
Department	N/A
[contact]

1.0 Purpose of the study:

The purpose of this 10-week feasibility study is to assess the tolerability, safety and efficacy of Transcranial LED Therapy for language learning and reducing symptoms of autism in children.

The investigators propose to enroll up to 30 participants, 2-7 years old, all of whom have recently completed the IRB approved study by JelikaLIt. They all have been previously diagnosed with moderate to severe ASD by licensed professionals according to the Diagnostic and Statistical Manual of Mental Disorders, Fifth Edition (DSM-5) criteria for Autism Spectrum Disorder (ASD).

This will be an one-arm, open label study. Participants who were in the placebo condition in the previous study, will receive the treatment. Participants who were in the active condition in the previous study will repeat the course of treatment after the intermission of 3-6 months (depending on when they completed the study).

The hypothesis to be tested is that exposure to photobiomodulation will reduce children's symptoms of autism, as measured by the reduction of the Mean Scores of the Childhood Autism Rating Scales, compared to the initial baseline.

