#### 5.0 Sample Size:

Up to 30 children will be included in the study. All the screening has been done already, as we anticipate bringing back the children who already participated in the previous study, described in 2.4 above.

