**7.0 Procedures Involved:**

7.1 Location: The study will use pre-test and post-test design. The entire study on the children will be done in the office. The weekly interview with the parent may be done either in office or by phone, as preferred by the parent.

7.2 Conditions: There will be only one active condition.

7.3 Participants: The participants will be 2 to 7 years old children previously diagnosed with moderate or severe ASD. Children of all genders and races will be included in this study.

7.4 Treatment: The treatment will take place twice a week for up to 30 minutes at a time.

During the study, while participants will be wearing the photobiomodulation device, they may be playing with their parent or the experimenter, using the toys of their choice (out of the many available in the experimenter's office). The caregivers will be present during the experiment at all times. When the child and the parent arrive, they will be welcomed to the office, and introduced to the toys.

The child will be encouraged to play with toys and interact with the parent (or the experimenter).

If the child becomes uncomfortable, the parents will be able to leave the experiment without any punishment. No coercion or deception is involved in this study.

7.5 Pre and Post-Testing:

The following measurements will be used for pretest and post-test.

- Childhood Autism Rating Scale (CARS2)

CARS 2 scores will be compared for analyses.

In addition, EEG will be collected from the participants pre and post -treatment in each session. Mobile FDA cleared EEG device from Brain Scientific will be used to collect children's pre and post test EEG.

There is no known danger of EEG collecting. In this study it will be using for measuring the efficacy treatment only.

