#### 14.0 Provisions to Protect the Privacy and Confidentiality of Participants and the Research Data:

Participants will be only interacting with [name], [name], Esq, or [name] (researcher). Participants and their parents will be tested individually, in a quiet room, and their confidentiality will be protected, as they won't be interacting with each other or with anybody else outside of the researchers.

The participants will be explained that they can refuse to answer any question. They can also refuse to participate in the study at any time. We do not anticipate uncomfortable questions, however, we will assure the participants that their level of comfort is of utmost importance, and we will explain to them that there is no penalty involved for their refusal to answer any specific question.

Only [name] and [name] will be able to access individual information. The participants will be immediately assigned Study ID number and only STUDY ID will be used for data analysis and reporting. Only aggregated data will be used for further reporting to the scientific community or to the business community. Individual data will be reported for illustrative purposes only with STUDY ID (not identifying personal information).

The following information will be included as data: Signed consent form (immediately scanned and stored in a cloud). Pre and Post-test Cars2 scores (with STUDY ID assigned). Weekly interview data (with STUDY ID assigned).

Identifying information will include Name and Age, Gender and number of therapy hours of the participant, Name and phone number of the parent. Children's age, gender and number of therapy hours will be used for matching purposes (for assigning to the control or treatment condition). Neither names of the participants nor names and phone numbers of their parents will be used for data analysis or reporting. Their names and phone numbers will be stored separately, in encrypted (password protected) file, in a secure cloud. Secure clouds as well as encryption and password protection will be used to protect identifying information.

The raw research data will be stored for 6 years. The identifying parental information will be kept for a year, for potential follow up interviews. The consent form will include their permission to keep identifying data for a year.

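### The consent discussion checks that parents understand a placebo group is possible, but the protocol defines a one-arm, open-label study with no placebo group

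*Protocol*

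**What the plan says.** Protocol section 10.0 describes the talk in which parental consent is obtained. Staff are to ask questions to make sure the parent has grasped a short list of points: that taking part is voluntary, "that the child may be placed in the placebo group", how much time is needed, and the possible risks and benefits.

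The design is set out elsewhere in the Protocol:

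- Section 1.0: "This will be an one-arm, open label study".
- Section 1.0, children formerly on placebo: "Participants who were in the placebo condition in the previous study, will receive the treatment".
- Section 1.0, children formerly on active: "Participants who were in the active condition in the previous study will repeat the course of treatment after the intermission of 3-6 months".
- Section 7.2: "There will be only one active condition".
- Section 5.0: "Up to 30 children will be included in the study", all expected to come from the study described in section 2.4.
- Section 7.4: "No coercion or deception is involved in this study".

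Two-group language also appears in three other places. Section 14.0 says that children's age, "gender and number of therapy hours will be used for matching purposes (for assigning to the control or treatment condition". Section 4.0, inclusion criterion 3, says the analysis will adjust for behavioural therapy in a control and an experimental condition. Section 7.6 says EEG will be collected from control and experimental groups and used to compare conditions.

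**The concern.** A statement in the consent discussion about what the child will receive should match the design. Here it does not. The mismatch is in one of the few points on which staff must actively confirm the parent's understanding, so it is not stray background text. A staff member who follows section 10.0 literally would be confirming a belief that is wrong under sections 1.0 and 7.2.

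What is at stake is the accuracy of the parent's decision about exposure. Section 3.0 says the device is neither approved nor marketed. The children are 2 to 7 years old, and section 10.0 says their own consent will not be obtained. Section 9.0 argues for the consent of one parent only. The conversation with that parent is therefore a main safeguard.

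Exposure also bears on risk in the protocol's own terms. Section 9.0 attributes the rare minor side effects to first-time users, and section 13.0 places transient effects at the start of treatment. Children formerly on sham would be first-time users of the active device, yet their parents would be told that placebo was possible.

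**Working it through.** No formula or power figure is involved. The check is whether any reading of the documents leaves room for a placebo group in this study.

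1. **Who can enter.** Inclusion criterion 9 in section 4.0 admits only children who took part in the previous trial, in its active or its placebo condition. There are two sources of participants and no third.
2. **What each source receives.** Section 1.0 covers both. Former placebo children are treated, and former active children repeat the course. No child is left without the active device.
3. **How many conditions there are.** Section 7.2 states one, and it is active. The text reviewed describes neither a randomisation procedure nor a sham device for this study.
4. **Chance of placebo under the stated design.** Section 2.4 gives 16 active and 14 sham children in the previous study. If all return, 16 + 14 = 30, the maximum in section 5.0. Of these, up to 14 would have a first active course and up to 16 a repeat course. Placebo allocations are 30 − 14 − 16 = 0, so the chance is 0 of up to 30. Section 10.0 presents it as possible.
5. **Whether the SAP supplies a placebo arm.** Its Primary Outcome section compares Active (n = 16) with Sham (n = 14). That is the same split that Protocol section 2.4 reports for the previous study, so it does not show a sham arm in this one.
6. **Whether the other two-group wording supplies one.** Sections 4.0, 7.6 and 14.0 mention control or experimental groups in passing. They conflict with sections 1.0 and 7.2 just as section 10.0 does. Three further inconsistencies do not outweigh two explicit statements of the design.
7. **The statement on deception.** Section 7.4 says there is none. Telling a parent that placebo is possible when it is not cannot be squared with that statement, whatever the reason for the wording.

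Steps 1 to 3 leave no placebo group, and steps 4 to 6 find nothing that restores one.

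**The case against.** The strongest reply is that one clause in the protocol's summary of the consent talk does not show what parents are told overall. Section 10.0 also says parents are debriefed on the purposes of the study, review the consent form and may ask questions. Section 8.0 refers to an attached consent script. Either document may describe the one-arm design correctly, and neither could be seen. This part of the objection stands, and it limits the finding to the instruction in section 10.0.

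Several stronger readings are tempting, but the documents do not support them:

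- *Parents sign a false description.* A reader might infer this, but the form was not available. Only the instruction for the conversation is shown to be wrong.
- *The wording was copied from an earlier randomised trial.* A leftover from the sham-controlled study is a natural explanation, but it remains an inference because that study's protocol is not available. No passage describes that study as randomised.
- *The sponsor intends to mislead.* Nothing suggests this. The clause reads more like an uncorrected leftover.
- *A mistaken belief about allocation biases the results.* Parents do keep the diary and give the weekly interviews, and section 15.0 uses the interviews for safety and efficacy. But section 7.6 treats the qualitative data as supplementary, section 15.0 plans no statistical analysis of the interview data, and the hypothesis is tested on CARS scores. No passage makes the diary or interviews the source of those scores. An effect on outcomes is conceivable but not demonstrated, and the point does not need it.
- *Section 14.0 misinforms families.* That sentence concerns data handling, and nothing says it is told to parents. It is a separate inconsistency of the same kind.

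**Conclusion.** The contradiction is direct, and no other text resolves it. Section 10.0 directs staff to confirm an incorrect point with the parent of every child, up to 30 families, when the chance of placebo under the stated design is 0. It is best classed as an internal inconsistency, since sections 1.0 and 7.2 state the design itself clearly. It must be fixed because the clause is an operative consent instruction about exposure to an unapproved device.

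The conclusion rests on sections 1.0 and 7.2 being the intended design. If the sponsor did mean to have a sham arm, those sections would be wrong instead, and the protocol would still need correcting before consent is taken. Confidence is high for the contradiction. No conclusion is drawn about the content of the signed form or the script, or about any effect on the data.

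**What to change.** - **Section 10.0:** replace the placebo clause with a statement that every child will receive the active device, that there is no placebo group, and that for children previously in the active condition this is a repeat course.
- **Consent form and consent script:** check both for the same wording and align them with section 1.0.
- **Section 14.0:** delete the sentence on matching for assignment to control or treatment.
- **Section 4.0 (inclusion criterion 3) and section 7.6 (EEG):** reconcile the control and experimental group wording with the one-arm design. If only section 10.0 were changed, the protocol would still contradict itself.

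No change to analysis covariates is part of this correction. The cost is a short text amendment across these sections with IRB notification. Sample size and study procedures are unaffected.

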## 11.0 Financial Compensation:

No financial compensation will be provided.

Parents of participants will be responsible for the cost of transportation to the research facilities. This is minimal risk to the participants.

## 12.0 Potential Benefits to Participants:

The possible benefit for the participant child may be improvement of speech, improvement of responsiveness, reduction of tantrums, reduction of anxiety, improvement of sleep, and improvement of eye contact.

### 13.0 Risks to Participants:

Potential Risks	Mitigating Factors
Some questions may be very personal or upsetting to the parents	Parents may skip any questions that they do not want to answer.
The child may feel uncomfortable wearing the headband and may want to take it off early	
If the child wants to take off the headband, we will first encourage him to wear it, by attempting to divert his attention to other things, such as toys and music.
 
If, however, the child insists on taking off the headband, he / she will not be forced to wear it and he / she may be able to take it off before the conclusion of the session.

Breach of confidentiality (child's data being seen by someone who shouldn't have access to it)	We'll keep all children identifying information separate from the research data, but we'll be able to link it by using a study ID. We will destroy this link after we finish collecting and analyzing the data.
The child maybe receiving concomitant medical treatment	Even though there are no interaction of the tPBM with any medications, children currently receiving any psychotropic medications on a regular basis, will be excluded from participating in this pilot-study. This will be determined during initial screening.
The child might be receiving behavioral Intervention such as ABA simultaneously with participating in the study.	
There is no known negative interaction of this treatment with any behavioral treatment.
 
The children should be able to receive their regular behavioral therapies while being enrolled in this study.
 
Clinicians will monitor (based on parental and therapists' interviews) each child's progress.

There may be risks that we do not know about yet. Exposure to LED lights is not known to have any negative side effects.	
After years of study, there are no known negative side effects of photobiomodulation.
 
Throughout the study, we'll tell parents if we learn anything that might affect their decision to let their child participate.
 
Minor transient side effects may include headaches, agitation, and hyper-activity. These side effects are sometimes observed in the beginning of the treatment and usually resolve on their own. Parents will be informed of these potential minor side-effects in the Consent form.

Some participants may have to be withdrawn from the study	If the child is not able to attend all the required sessions and the caregiver is not able to reschedule a cancelled session within a 7-day window, then the child may have to be withdrawn from the study.

	
 
1. If the child has completed at least 8 weeks, we will ask them to do final assessments and this data will be included in the final analysis.
 
2. If the child has completed less than 8 weeks and missed a week due to sickness, the family will be offered to restart the 12-week course. Regardless of the outcome, we will ask the child's parents for permission to contact them in the future with follow up questions regarding the child's behavior.
 

--	-------------------------------------------------------------------------------------------------------------------------------------------------------------------------------------------------------------------------------------------------------------------------------------------------------------------------------------------------------------------------------------------------------------------------------------------------------------------------------------------------------------------------

#### 14.0 Provisions to Protect the Privacy and Confidentiality of Participants and the Research Data:

Participants will be only interacting with [name], [name], Esq, or [name] (researcher). Participants and their parents will be tested individually, in a quiet room, and their confidentiality will be protected, as they won't be interacting with each other or with anybody else outside of the researchers.

The participants will be explained that they can refuse to answer any question. They can also refuse to participate in the study at any time. We do not anticipate uncomfortable questions, however, we will assure the participants that their level of comfort is of utmost importance, and we will explain to them that there is no penalty involved for their refusal to answer any specific question.

Only [name] and [name] will be able to access individual information. The participants will be immediately assigned Study ID number and only STUDY ID will be used for data analysis and reporting. Only aggregated data will be used for further reporting to the scientific community or to the business community. Individual data will be reported for illustrative purposes only with STUDY ID (not identifying personal information).

The following information will be included as data: Signed consent form (immediately scanned and stored in a cloud). Pre and Post-test Cars2 scores (with STUDY ID assigned). Weekly interview data (with STUDY ID assigned).

Identifying information will include Name and Age, Gender and number of therapy hours of the participant, Name and phone number of the parent. Children's age, gender and number of therapy hours will be used for matching purposes (for assigning to the control or treatment condition). Neither names of the participants nor names and phone numbers of their parents will be used for data analysis or reporting. Their names and phone numbers will be stored separately, in encrypted (password protected) file, in a secure cloud. Secure clouds as well as encryption and password protection will be used to protect identifying information.

The raw research data will be stored for 6 years. The identifying parental information will be kept for a year, for potential follow up interviews. The consent form will include their permission to keep identifying data for a year.

Although we do not plan to re-contact the participants after the study is complete, a follow up interview in 6 months or a year could be useful to assess the sustainability of the benefits of photobiomodulation. In this case, we will be applying for a separate IRB (minimal risks) to conduct the follow up interview. Presently, we do not plan to do it (although we recognize that it could potentially be useful for research purposes).

The data will be stored in encrypted, password protected files in a secure cloud.

